10.4.3. Collection of Pregnancy Information:**Male participants with partners who become pregnant**

- Investigator will attempt to collect pregnancy information on any male participant's female partner who becomes pregnant while participating in this study. This applies only to male participants who receive study intervention.
- After obtaining the necessary signed informed consent from the pregnant female partner directly, the investigator will record pregnancy information on the appropriate form and submit it to GSK within 24 hours of learning of the partner's pregnancy.
- The female partner will also be followed to determine the outcome of the pregnancy. Information on the status of the mother and child will be forwarded to GSK.
- Generally, follow-up will be no longer than 6 to 8 weeks following the estimated delivery date. Any termination of the pregnancy will be reported regardless of fetal status (presence or absence of anomalies) or indication for procedure

10.5. Appendix 5: Genetics

- **USE/ANALYSIS OF DNA** Genetic variation may impact a participant's response to study intervention, susceptibility, severity and progression of disease. Variable response to study intervention may be due to genetic determinants that impact drug absorption, distribution, metabolism, and excretion; mechanism of action of the drug; disease etiology; and/or molecular subtype of the disease being treated. Therefore, where local regulations and IRB/IEC allow, a blood sample will be collected for DNA analysis
- DNA samples will be used for research related to study intervention. They may also be used to develop tests/assays including diagnostic tests) related to study intervention]. Genetic research may consist of the analysis of one or more candidate genes or the analysis of genetic markers throughout the genome [or analysis of the entire genome (as appropriate)
- Additional analyses of DNA samples may be conducted if it is hypothesized that this may help further understand the clinical data.
- The sponsor will store the DNA samples in a secure storage space with adequate measures to protect confidentiality.
- The samples will be retained while research on study intervention (or study interventions of this class) continues but no longer than 15 years after the last subject last visit or other period as per local requirements.

10.6. Appendix 6: Liver Safety: Required Actions and Follow-up Assessments

Phase 1 Liver chemistry stopping criteria have been designed to assure subject safety and to evaluate liver event aetiology.

Phase 1 liver chemistry stopping criteria and required follow up assessments

Liver Chemistry Stopping Criteria	
ALT-absolute ALT \geq 3xULN If ALT \geq 3xULN AND bilirubin ^{1,2} \geq 2xULN (>35% direct bilirubin) or international normalized ratio (INR) >1.5 , Report as an SAE. See additional Actions and Follow Up Assessments listed below	
Required Actions and Follow up Assessments	
Actions	Follow Up Assessments

 Immediately discontinue study intervention Report the event to GSK within 24 hours Complete the liver event CRF, and complete an SAE data collection tool if the event also meets the criteria for an SAE² Perform liver event follow up assessments Monitor the participant until liver chemistries resolve, stabilise, or return to within baseline (see MONITORING below) 
MONITORING:
 
If ALT\geq3xULN AND bilirubin \geq 2xULN or INR >1.5
 
 Repeat liver chemistries (include ALT, aspartate transaminase [AST], alkaline phosphatase, bilirubin and INR) and perform liver event follow up assessments within 24 hours Monitor participant twice weekly until liver chemistries resolve, stabilise or return to within baseline A specialist or hepatology consultation is recommended 	
 Viral hepatitis serology³ Obtain INR and recheck with each liver chemistry assessment until the transaminases values show downward trend Obtain blood sample for pharmacokinetic (PK) analysis as soon as possible, and at least within 7 days, post last dose⁴ Serum creatine phosphokinase (CPK) and lactate dehydrogenase (LDH). Fractionate bilirubin, if total bilirubin\geq2xULN Obtain complete blood count with differential to assess eosinophilia Record the appearance or worsening of clinical symptoms of liver injury, or hypersensitivity, on the AE report form Record use of concomitant medications on the concomitant medications report form including acetaminophen, herbal remedies, other over the counter medications. Record alcohol use on the liver event alcohol intake case report form

Liver Chemistry Stopping Criteria	

If $ALT \geq 3 \times ULN$ AND bilirubin < $2 \times ULN$ and INR ≤ 1.5:
 
 • Repeat liver chemistries (include ALT, AST, alkaline phosphatase, bilirubin and INR) and perform liver event follow up assessments within 24-72 hours • Monitor participant weekly until liver chemistries resolve, stabilize or return to within baseline 	
If $ALT \geq 3 \times ULN$ AND bilirubin $\geq 2 \times ULN$ or INR > 1.5:
 
 • Anti-nuclear antibody, anti-smooth muscle antibody, Type 1 anti-liver kidney microsomal antibodies, and quantitative total immunoglobulin G (IgG) or gamma globulins. • Serum acetaminophen adduct high performance liquid chromatography (HPLC) assay (quantifies potential acetaminophen contribution to liver injury in subjects with definite or likely acetaminophen use in the preceding week) [James, 2009]. • Liver imaging (ultrasound, magnetic resonance, or computerised tomography) and /or liver biopsy to evaluate liver disease; complete Liver Imaging and/or Liver Biopsy CRF forms.

1. Serum bilirubin fractionation should be performed if testing is available. If serum bilirubin fractionation is not immediately available, discontinue study intervention for that subject if $ALT \geq 3 \times ULN$ and $bilirubin \geq 2 \times ULN$. Additionally, if serum bilirubin fractionation testing is unavailable, record presence of detectable urinary bilirubin on dipstick, indicating direct bilirubin elevations and suggesting liver injury.
2. All events of $ALT \geq 3 \times ULN$ and $bilirubin \geq 2 \times ULN$ ($> 35\%$ direct bilirubin) or $ALT \geq 3 \times ULN$ and $INR > 1.5$, which may indicate severe liver injury (possible 'Hys Law'), must be reported as an SAE (excluding studies of hepatic impairment or cirrhosis); the INR threshold value stated will not apply to subjects receiving anticoagulants
3. Includes: Hepatitis A immunoglobulin (gm) antibody; HBsAg and HBcAb; Hepatitis C RNA; Cytomegalovirus IgM antibody; Epstein-Barr viral capsid antigen IgM antibody (or if unavailable, obtain heterophile antibody or monospot testing) and Hepatitis E IgM antibody
4. PK sample may not be required for participants known to be receiving placebo or non-GSK comparator interventions. Record the date/time of the PK blood sample draw and the date/time of the last dose of study intervention prior to PK blood sample draw on the CRF. If the date or time of the last dose is unclear, provide the participant's best approximation. If the date/time of the last dose cannot be approximated OR a PK sample cannot be collected in the time period indicated above, do not obtain a PK sample. Instructions for sample handling and shipping are in the SRM

10.7. Appendix 7: Abbreviations and Definitions and Trademarks

Abbreviations

ADA	Anti-Drug Antibody
AE	Adverse Event
AUC	Area Under the concentration-time Curve
BMI	Body Mass Index
BUN	Blood Urea Nitrogen
CA	Competent Authority
CCL17	Chemokine C-C motif ligand 17
CFR	Code of Federal Regulation
CIOMS	Council for International Organizations of Medical Sciences
Cmax	Maximum Observed Concentration
CONSORT	Consolidated Standards of Reporting Trials
COVID-19	Coronavirus Disease 2019
CPK	Creatine Phosphokinase
CRF	Case Report Form
CSR	Clinical Study Report
EC	Ethics Committee
ECG	Electrocardiogram
eCRF	Electronic Case Report Form
EMA	European Medicines Agency
FDA	Food and Drug Administration
FiH	First in Human
GCP	Good Clinical Practice
GSK	GlaxoSmithKline
HBcAb	Hepatitis B Core Antibody
HBsAg	Hepatitis B Surface Antigen
HIV	Human Immunodeficiency Virus
HPLC	High-Performance Liquid Chromatography
IB	Investigator's Brochure
ICF	Informed Consent Form
ICH	International Conference on Harmonisation of Technical Requirements for Registration of Pharmaceuticals for Human Use
IEC	Independent Ethics Committee
IgA	Immunoglobulin A
IgM	Immunoglobulin G
INR	International Normalized Ratio
IP	Investigational Product
IRB	Institutional Review Board
IWRS	Interactive Web Recognition System
kg	Kilogram
LDH	Lactate Dehydrogenase
mAb	Monoclonal Antibody
MCH	Mean Corpuscular Haemoglobin

MRCT	Multiregion Randomised Clinical Trial
MCV	Mean Corpuscular Volume
mg	Milligram
mL	Milliliter
MSDS	Material Safety Data Sheet
NIMP	Non-Investigational Medicinal Product
NSAID	Non-Steroidal Anti-Inflammatory Drug
OA	Osteoarthritis
PBO	Placebo
PGx	Genetics Sample
PD	Pharmacodynamics
PK	Pharmacokinetics
PPE	Personal Protective Equipment
QTc	Electrocardiogram QT interval corrected for heart rate
QTcB	Electrocardiogram QT interval corrected for heart rate using Bazett's formula
QTcF	Electrocardiogram QT interval corrected for heart rate using Fridericia's formula
RAMOS NG	Randomization and Medication Ordering System Next Generation
RAP	Reporting and Analysis Plan
RBC	Red Blood Cells
RNA	Ribonucleic Acid
SAE	Serious Adverse Event
SARS-CoV-2	Severe acute respiratory syndrome- Coronavirus-2
SC	Subcutaneous
sec	Seconds
SGOT	Serum Glutamic-Pyruvic Transaminase
SGPT	Serum Glutamic-Pyruvic Transaminase
SMG	Safety and Medical Governance
SRM	Study Reference Manual
SoA	Schedule of Activities
TARC	Thymus and Activation Regulated Chemokine
TB	Tuberculosis
TDAR	T-cell Dependent Antibody Response
TE	Target Engagement
tmax	Time of Occurrence of Maximum Observed Drug Concentration
UACR	Urine albumin-creatinine ratio
UK	United Kingdom
ULN	Upper Limit of Normal
WBC	White Blood Cells
WOCBP	Woman of Childbearing Potential
WONCBP	Woman of Non-childbearing Potential

10.8. Amendment History

The Protocol Amendment Summary of Changes Table for the current amendment is located directly before the Table of Contents (TOC).

Amendment 1 11-JAN-2022

Overall Rationale for the Amendment:

This is a protocol amendment with changes to the inclusion/exclusion criteria, assessment time points, clarification regarding consent to further research, clarification regarding alcohol consumption and tobacco use, changes to the protocol title to align with eTrack and correction of typographical errors. These amendments were made following feedback from the study site and HREC.

Section # and Name	Description of Change	Brief Rationale
Global Change	Troponin-T updated to Troponin I" throughout protocol	Troponin T and Troponin I have similar diagnostic accuracy.
1.1 Overall Design	Updated text – 'To try to eliminate any time dependant variability among ethnic groups, we will aim to treat Caucasian and Asian groups concurrently.	This amendment was made for clarification
1.3 Schedule of Activities	Estradiol removed from screening period table	FSH is sufficient to confirm menopause as specified in Section 10.4
1.3 Schedule of Activities	CCI [REDACTED] [REDACTED]	Aid with participant compliance to the study schedule.
1.3 Schedule of Activities	Outpatient visit removed from Day -1.	Error in original protocol. Participants will be admitted on Day -1 for an overnight stay.
1.3 Schedule of Activities	Footnotes 4 and 5 removed from Day -1 12 Lead ECG and Vital signs tests	These were present in error in the original protocol.
1.3 Schedule of Activities	COVID PCR, footnote 7 removed from Day 57, CCI and Early Withdrawal visits.	Error in original protocol, footnote applies to Day -2 visit only
1.3 Schedule of Activities - PD	Footnote 10 removed from Day 1 for Serum/Plasma for protein and PD for transcriptomic analysis.	Error in original protocol, footnote 10 applies to PK and TE samples only.
5.1 Inclusion Criteria	Inclusion Criteria #5 Updated to widen the BMI range for Caucasian participants	This amendment was made to maximise the Caucasian participant pool.
5.2 Exclusion Criteria	Exclusion Criterion #12. Typographical error Bazett's" formula is shown as QTcF in protocol, this has been corrected to QTcB	This amendment was made to correct typographical errors.
5.2 Exclusion Criteria	Exclusion Criterion #18 - Added details about enzyme inducers and allowed medications directly into the exclusion criteria	This will ensure that participants are not included in the study when they are not allowed or excluded when they could potentially be eligible.

Section # and Name	Description of Change	Brief Rationale
5.2 Exclusion Criteria	Exclusion Criterion #35 – Amended the definition of an average weekly intake of alcohol to: >11 standard drinks for males and females. One standard drink contains 10g of alcohol	This amendment was made as requested by HREC
5.3.3 Caffeine Alcohol and Tobacco	Text updated 'participants should not consume more 1.5 standard drinks of alcohol daily on average (10g alcohol in 1 Australian standard drink)'	This amendment was made as requested by HREC
5.3.3 Caffeine Alcohol and Tobacco	Protocol text update adding 'Non-smokers or light smokers <= 5 cigarettes / nicotine-forms per week) may be enrolled in the trial. Light smokers must abstain from nicotine containing products for at least 3 days prior to Day 1 dosing and for the duration of the inpatient stay'	Updated text to allow light smokers to participate in the study
8.2.2. Vital Signs	Text added to state the average of triplicate blood pressure measurements confirms participant eligibility.	This amendment was made for clarification
10.1.3 Informed Consent Process	Updated the protocol text replacing the requirement for a separate signature in the ICF to allow use of participant data and/or remaining leftover samples to be used for further research not related to the study/disease with a tick corresponding 'Yes' box	This amendment clarified the inconsistency in wording regarding consent between the ICF and the protocol for further use of participant data and or remaining leftover sample.
Appendix 2: Clinical Laboratory Tests	Table 2: Test for estradiol levels removed.	FSH is sufficient to confirm menopause as specified in Section 10.4

Section # and Name	Description of Change	Brief Rationale
Trademark Information	Additional table added for Trademarks not owned by the GlaxoSmithKline group of companies	Amendment made as requirement of protocol template

Trademark Information

Trademarks of the GlaxoSmithKline group of companies	Trademarks not owned by the GlaxoSmithKline group of companies
RAMOS NG	None

6.2.2.	Study Phase	25
6.2.3.	Study Day and Reference Dates	25
6.2.4.	Assessment Window	26
6.2.5.	Multiple measurements at One Analysis Time Point	26
6.2.6.	Handling of Partial Dates	26
7.	REFERENCES.....	29

Version history

SAP Version	Approval Date	Protocol Version (Date) on which SAP is Based	Change	Rationale
SAP	10 May 2022	Protocol Amendment 02 (29-APR-2022)	Not Applicable	Original version
SAP Amendment 1	28 Nov 2022	Protocol Amendment 02 (29-APR-2022)	Update to Objectives and Endpoints table	Changes to objectives not made in original version following protocol amendment 2
			Removal of sentence specifying Anatomical Therapeutic Chemical (ATC) classifications will not appear in summaries	Decision to include ATC classifications in summaries
			Inclusion of details of additional interim analysis	Decision made to conduct additional interim analysis for this study to support regulatory submissions

1. INTRODUCTION

The purpose of this SAP is to describe the planned analyses to be included in the CSR for Study 212979.

1.1. Objectives, Estimands and Endpoints

Objectives	Endpoints
Primary	

 To evaluate the safety and tolerability of a single SC dose of GSK3858279 compared with placebo administered to healthy participants including cohorts of Japanese, Chinese and Caucasians 	
 Incidence of adverse events (AEs), serious adverse events (SAEs), withdrawals due to AEs Occurrence of clinically important changes from baseline in clinical laboratory parameters (haematology, clinical chemistry, urinalysis), vital signs (blood pressure, heart rate, body temperature), and cardiac parameters (electrocardiogram)

 To assess the pharmacokinetic (serum PK) profile up to 56 days following a single SC dose of GSK3858279 in healthy participants including cohorts of Japanese, Chinese and Caucasians 	
 PK parameters: area under the concentration-time curve (AUC(0-56), AUC(0-t) post-dose), time of occurrence of last quantifiable concentration (t_{last}), maximum observed concentration (C_{max}), and time of occurrence of C_{max} (t_{max}) per cohort as data permits
Secondary	

 To evaluate target engagement (TE) up to 56 days following a single SC dose of GSK3858279 in healthy participants including cohorts of Japanese, Chinese and Caucasians. 	
 Reduction (%) from baseline in free CCL17: maximum, minimum and at Days 7, 14, 28 and 56 post-dose Total CCL17 (free and when bound to GSK3858279): maximum observed concentration (C_{max}), time of C_{max} (t_{max}), maximum fold increase compared to baseline, fold increase compared to baseline at Days 7, 14, 28 and 56 post-dose.

 To assess the potential for anti-drug 	
 Incidence of pre-existing ADAs

Objectives	Endpoints
antibody (ADA) formation	
• Incidence of treatment-emergent ADAs over time (and whether neutralising)
Exploratory	

CCI

1.2. Study Design

Overview of Study Design and Key Features	
CCI	
Design Features	
• This is a Ph1 Randomised, Double-blind, Placebo-controlled Study of the Safety, Tolerability, Pharmacokinetics, Target Engagement and Immunogenicity of a single subcutaneous dose of GSK3858279 administered to Healthy Caucasian, Chinese and Japanese Participants.• The total duration of this study is not expected to exceed a maximum of CCI [redacted]: (Screening [up to 28 days] and a follow-up period of CCI [redacted]). Follow-up may be extended if a serious or clinically significant AE CCI [redacted].• The primary PK and TE analysis for this study will occur once all participants have completed Day 57. An interim analysis of safety will also be conducted at this time.
Study intervention	Study intervention will be administered on Day 1 as four separate SC injections of either GSK3858279 (CCI [redacted] or Placebo.
Study intervention Assignment	Cohorts of Caucasian, Chinese and Japanese participants will be randomised to GSK3858279 CCI [redacted] or Placebo in a 7:3 ratio, respectively for each cohort.
Interim Analysis	Interim analysis of Safety data will occur alongside primary PK and TE analysis at Day 57. Additional interim analyses may be performed on data assessed in an unblinded manner, to support regulatory submissions. No changes to the conduct of the study will be implemented as a result of the analyses.

2. STATISTICAL HYPOTHESES

The co-primary objectives of this study are:

- To evaluate the safety and tolerability of a single SC dose of GSK3858279 compared with placebo administered to healthy participants including cohorts of Japanese, Chinese and Caucasians
- To assess the pharmacokinetic (PK) profile of a single SC dose of GSK3858279 in healthy participants including cohorts of Japanese, Chinese and Caucasians

No formal statistical hypotheses will be tested.

2.1. Multiplicity Adjustment

There will be no adjustments for multiplicity.

3. ANALYSIS SETS

Analysis Set	Definition / Criteria	Analyses Evaluated
Screened	All participants who were screened for eligibility.	Study Population
Enrolled	
All participants who entered the study, signed the ICF and were eligible for randomisation (regardless of whether the participant went on to be randomised).
 
Note screening failures (who never passed screening even if rescreened) and participants screened but never enrolled into the study (met eligibility but not needed) are excluded from the Enrolled analysis set as they did not enter the study.
	Study Population
Randomised	
All participants who were randomly assigned to study intervention in the study.
 
Data will be reported according to the randomised study intervention.
	Study Population
Safety	
All participants who received at least one injection of study intervention.
 
Data will be reported according to the actual study intervention received.
	Safety
Pharmacokinetic (PK)	
All participants in the safety population who received an active dose of study treatment and had at least one reportable PK assessment (Non-quantifiable [NQ] values will be considered as reportable values).
 
Participants will be analysed according to the study intervention they actually received.
	PK
Target Engagement (TE)	
All participants in the safety population who had at least one reportable TE assessment (Non-quantifiable [NQ] values will be considered as reportable values).
 
Participants will be analysed according to the study intervention they actually received.
	TE

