4.1. Overall Design

This is a randomised, double-blind, placebo-controlled, multi-centre study with a single SC dose of GSK3858279 administered to healthy Caucasian, Chinese and Japanese participants.

[figure not shown]
- Participants will attend a screening visit at the clinical units within 28 days of Study Day 1. If eligible for the study, participants will return on Day -1 and will be admitted to the unit overnight for final screening checks in preparation for randomization and dosing (Day 1).
- Participants will be randomized to either GSK3858279 or placebo in a ratio of 7:3 per cohort.
- Each participant will receive a **CCI** SC dose of GSK3858279 or placebo, administered as four separate SC injections.
- Participants will then remain as an inpatient until discharged on Day 3 after assessments have been performed.
- Participants will then return to the clinical unit for outpatient visits as described in the SoA.
 - It will be mandatory for the Caucasian cohort to continue **CCI**, where they will have their final follow up visit at the clinical unit. The final required follow up visit will be at the clinical unit on **CCI** for Chinese and Japanese participants. NB: Japanese and Chinese participants have an option to remain in the study until **CCI**
 - The maximum dose will not exceed **CCI** SC

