7. DISCONTINUATION OF STUDY INTERVENTION AND PARTICIPANT DISCONTINUATION/WITHDRAWAL

7.1. Discontinuation of Study Intervention

This is a single dose study. In rare instances a participant may not be able to receive the 4 injections and it may be necessary for the participant to permanently discontinue study intervention. If study intervention is discontinued, the participant will remain in the study for the planned duration.

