4. STATISTICAL ANALYSES

4.1. General Considerations

4.1.1. General Methodology

Participants who withdraw from the study may be replaced, with any replacements beginning from the start of the study.

Summary tables will provide the following descriptive statistics as a minimum, unless otherwise specified:

- Continuous data (normally distributed):
n, mean, standard deviation (SD), median, minimum and maximum.
- Continuous data (log-normally distributed):
n, geometric mean, SD on the log scale (SD (log)), median, minimum and maximum.
- Categorical data:
number and percentage of participants in each category.

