5. SAMPLE SIZE DETERMINATION

Approximately 10 participants are to be randomized (7 active: 3 placebo) per cohort to ensure that a minimum of 6 participants on active and 2 on placebo per cohort are evaluable. An evaluable participant is one that has been dosed and has safety and all PK data up to Day 57. Replacements (assigned to the same treatment) are permitted at the discretion of the sponsor in consultation with the investigator.

[figure not shown]
CCI

CCI

CONFIDENTIAL

212979

CCI

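### Does the undefined term active dose in the PK set leave it open whether a partly dosed participant enters the AUC(0-56) and Cmax models?

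*SAP*

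**What the plan says.** The PK set in SAP section 3, repeated in protocol 9.2, is "All participants in the safety population who received an active dose of study treatment and had at least one reportable PK assessment". It is built on the Safety set, which is "All participants who received at least one injection of study intervention". The design text describes what is given as a "SC dose of GSK3858279 or placebo, administered as four separate SC injections" (protocol 4.1; SAP 1.2 agrees).

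Protocol 7.1 allows for incomplete dosing: "In rare instances a participant may not be able to receive the 4 injections". In that event "the participant will remain in the study for the planned duration", so PK sampling continues.

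SAP 4.2.1 runs every PK analysis on the PK population. SAP 4.2.1.2 models log AUC(0-56) and log Cmax on ethnicity and log body weight, and again on ethnicity alone. Neither model has a dose term, and SAP 4.2.3 plans no formal sensitivity analysis.

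For sample size, SAP section 5 says "An evaluable participant is one that has been dosed and has safety and all PK data up to Day 57", again without a number of injections.

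**The concern.** The Safety set counts injections, while the next row of the same table switches to a dose and stops counting. If a dose means the four-injection administration of the design sections, someone given two injections is out of the PK set. If the word active only separates drug from placebo, that person is in.

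The study estimates Japanese/Caucasian and Chinese/Caucasian exposure ratios after one fixed dose, with about 7 active participants per cohort. One low exposure caused by incomplete dosing would be read by the model as an ethnic difference. In the Caucasian cohort it would move both reported ratios together. These ratios are meant to support Chinese and Japanese participation in later studies, so an open choice between two analysis sets deserves a check.

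**Working it through.** **Which reading the text supports.** The PK and TE rows of SAP section 3 can be set side by side.

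| | PK set | TE set |
|---|---|---|
| Starting point | Safety population | Safety population |
| Extra condition | received an active dose | none |
| Data needed | one reportable PK assessment, non-quantifiable values count | one reportable TE assessment, non-quantifiable values count |

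Apart from the type of assessment, the only difference is the active-dose condition. The TE set keeps placebo participants and the PK set does not, so the condition acts as a placebo filter. Active is also the arm name in protocol Table 1 and in the 7 active to 3 placebo allocation. The injection threshold is set one level up, at one injection. An unstated four-injection threshold would sit oddly in a set that one non-quantifiable value is enough to enter. On this reading the partly dosed active participant is in the PK set.

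**What that does to the estimates.** The documents give no figure to reproduce, because the sample-size assumptions are redacted. The inputs are:
- n = 7 active per cohort, minimum 6 (SAP section 5).
- f = 3/4, 2/4 or 1/4 of the dose, in one participant.
- Assumed, not in the documents: equal drug per injection, dose-proportional exposure, and a between-subject CV of 30% (range 20-40%).

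In the ethnicity-only model the cohort geometric mean is multiplied by f^(1/n):
- n = 7: 0.75^(1/7) = 0.960; 0.5^(1/7) = 0.906; 0.25^(1/7) = 0.820.
- n = 6: 0.953; 0.891; 0.794.

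If the participant is Caucasian, both ratios are multiplied by the inverse. For n = 7 that is 1.042, 1.104 or 1.219.

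The 90% CI for a ratio is the estimate times or divided by exp(t(0.95, 3(n-1)) × s × sqrt(2/n)), with s = sqrt(ln(1 + CV²)). The partly dosed participant adds ln(f)² × (1 - 1/n) / (3(n-1)) to the expected pooled variance. For n = 7:

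| CV | All fully dosed | 3 of 4 | 2 of 4 | 1 of 4 |
|---|---|---|---|---|
| 20% | 1.201 | 1.212 | 1.260 | 1.398 |
| 30% | 1.313 | 1.321 | 1.358 | 1.478 |
| 40% | 1.429 | 1.436 | 1.468 | 1.575 |

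At CV 30%, the ratio shifts of 1.04, 1.10 and 1.22 are all smaller than the CI factor of 1.313 that applies with everyone fully dosed.

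In the weight-adjusted model the average shift is the same, but it varies with that participant's weight. With assumed mean weights of 78/65/63 kg (SD 9), CV 30% and 8,000 simulated trials per setting, the 5th to 95th percentiles of the shift are 1.01-1.08, 1.02-1.20 and 1.05-1.44. Coverage of the 90% CI is 0.900, 0.891 and 0.882.

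**What leaving the participant out would cost.** In the weight-adjusted model, ignoring covariate imbalance, t × sqrt(1/na + 1/nb) goes from 0.930 (7 v 7, 17 df) to 0.971 (6 v 7, 16 df). The interval is about 4% wider.

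**Whether the case would be noticed.** In the ethnicity-only model, incomplete dosing moves that participant's residual on average by ln(f) × (1 - 1/n). For n = 7 this is -0.288 × 6/7 = -0.25, -0.693 × 6/7 = -0.59, or -1.386 × 6/7 = -1.19. With s = sqrt(ln 1.09) = 0.294, these are about 0.8, 2.0 and 4.0 SDs. The residual plots required by SAP 4.2.1.2 would tend to show the larger distortions. The dosing record (protocol 6.4) would show all of them.

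**The evaluable count.** An evaluable participant needs all PK data to Day 57, whereas the PK set needs one assessment. The two counts can differ however many injections the word dosed implies, so defining that word would not tie the minimum of 6 to the number in the models.

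**The case for a change.** The best opposing argument is about timing. Even if the participant is clearly in the PK set, a reduced dose then enters a fixed-dose comparison unadjusted, and nothing says whether the models should keep, drop or dose-normalise that person. SAP 4.7 unblinds the biostatistics and CPMS teams at interim analyses, and 4.7.2 allows one before the primary PK analysis with individual data. The choice could therefore be made by people who have seen the concentrations. The deviation review in SAP 6.1.3 precedes unblinding and database freeze, but it assigns nobody to an analysis set.

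This is correct as far as it goes: no readable passage gives the model-level rule. Its weight is limited. The number of injections is fixed on Day 1, when a second staff member confirms the dose, and does not depend on any concentration. Parameters are listed per participant (SAP 4.2.1.1), and protocol section 9 requires departures from the planned analyses to go into a SAP addendum or be justified in the study report.

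The obvious remedy, a PK set restricted to four injections, would go against the more natural reading. Because all PK analyses use that set, it would also remove the participant from the concentration summaries and the descriptive AUC, Cmax, tmax and tlast summaries. The dosing-instruction row of protocol Table 1 is redacted, so a rule there cannot be ruled out.

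**Conclusion.** No change follows. The PK set can be read without strain: any active injection qualifies. The remaining gap is how the two ethnicity models treat a partly dosed participant, in an event the protocol calls rare and gives no frequency for, under supervised single-day dosing. Analysts would know of the case from the dosing record, and keeping, dropping or dose-normalising that participant in the models is a matter of preference.

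If one of 7 active participants were affected, the cohort geometric mean would be multiplied by 0.96, 0.91 or 0.82 for 3, 2 or 1 of 4 injections, assuming equal drug per injection and dose-proportional exposure. The larger figures need half or more of the dose to be missed. Leaving the participant out would widen the interval by about 4%. The comparison is estimation only, with no hypothesis test that could turn on the choice.
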